#### Comparator agents:

Initiators of ACEi, any dose and frequency.

### 6.2 Preliminary Covariates:

- Age

- Sex
- Combined Comorbidity Index (CCI), measured over the default baseline covariate assessment period of 180 days prior to and including the index prescription date

Covariates listed above are a small subset of covariates that will ultimately be controlled in the design and analysis phase of the study. They are included in the preliminary assessment to determine the presence of adequate overlap between the two population of patients to proceed to the next phase of the study. Remaining covariates are defined only after the study has passed the initial feasibility analysis and initial power assessment and are listed in Table 1 (**Appendix B**).

### 6.3 Outcome variables and study follow-up:

#### 6.3.1 Outcome variables

Effectiveness outcome variables of interest (definitions provided in **Appendix A**):

- **Primary outcome:** Composite of hospitalization for heart failure and all-cause mortality
- Secondary outcomes:
  - Heart failure hospitalization
  - All-cause death

Control outcomes of interest (control outcomes only serve to assess aspects of study validity but are not further interpreted, definitions provided in Appendix A):

1. Bleeding (we expect to see a null association, as renin angiotensin aldosterone inhibitors are not expected to have any impact on this outcome)

#### 6.3.2 Study follow-up

Both as-treated (AT) and intention-to-treat (ITT) analysis will be conducted with treatment defined as the index drug on the day of cohort entry. Because adherence in the real-world databases is expected to be much worse than in the trial, the AT analysis is the **primary** analysis, as it targets the relative hazard of outcomes on treatment.

For the AT analysis, the follow-up will start the day after the initiation of sacubitril/valsartan or ACEi and will continue until the earliest date of the following events:

- The first occurrence of the outcome of interest,
- The date of end of continue registration in the database,
- End of the study period,
- Nursing home admission
  - Nursing home admissions are considered a censoring event because the data sources utilized typically provide little to no data on a patient, particularly on drug utilization, after admission. We will utilize this as an exclusion reason for cohorts for the same reason.
- The date of drug discontinuation, defined as the date of the last continuous treatment episode of the index drug (sacubitril/valsartan or ACEi) + a 30-day grace period,
- The date of switching from an exposure to comparator and vice versa,
- The date of switching to or initiation of any angiotensin II receptor blockers (ARBs), including combination medications containing ARBs,
- The date of switching to or initiation of aliskiren, including combination therapies.

For the ITT analyses, the censoring based on the switching and treatment discontinuation will be replaced with a maximum allowed follow-up time of 365 days.

## 7 Initial Feasibility Analysis

Action report name:

Optum- <https://bwh-dope.aetion.com/projects/details/1069/results/61863/result/0>

MarketScan- <https://bwh-dope.aetion.com/projects/details/1072/results/61852/result/0>

Medicare - <https://bwh-dope.aetion.com/projects/details/1073/results/61854/result/0>

Date conducted: 11/24/2020

Complete Action feasibility analysis using age, sex, and CCI as the only covariates and the primary endpoint (Section 6.3.1) as the outcome.

- Complete study flowchart from Section 5.3
- Report patient characteristics by treatment group

	Optum	MarketScan	Medicare
--	-------	------------	----------

Variable	Reference - ACE inhibitors	Exposure - Sacubitril/valsartan	Difference	Reference - ACE inhibitors	Exposure - Sacubitril/valsartan	Difference	Reference - ACE Inhibitors	Exposure - Sacubitril/valsartan Copy	Difference
Number of patients	4,217	2,729	-	2,218	1,476	-	6,293	1,738	-
Age									
...mean (sd)	66.94 (13.39)	68.39 (12.07)	-1.45 (-2.06, -0.84)	60.86 (14.92)	61.21 (13.50)	-0.36 (-1.29, 0.57)	77.16 (8.29)	76.04 (7.56)	1.12 (1.5)
...median [IQR]	68.00 [58.00, 77.00]	70.00 [61.00, 77.00]	-	60.00 [52.00, 71.00]	60.00 [53.00, 70.00]	-	76.00 [70.00, 84.00]	75.00 [70.00, 81.00]	-
Gender									
..Males; n (%)	2,829 (67.1%)	1,773 (65.0%)	2.1% (-0.2%, 4.4%)	1,606 (72.4%)	1,018 (69.0%)	3.4% (0.4%, 6.5%)	3,433 (54.6%)	1,003 (57.7%)	-3.2% (-0.5%)
...Females; n (%)	1,388 (32.9%)	956 (35.0%)	-2.1% (-4.4%, 0.2%)	612 (27.6%)	458 (31.0%)	-3.4% (-6.5%, -0.4%)	2,860 (45.4%)	735 (42.3%)	3.2% (5.8%)
CCI (180 days)- ICD9 and ICD10 v2									
...mean (sd)	6.52 (2.50)	6.70 (2.24)	-0.18 (-0.29, -0.06)	5.51 (2.22)	5.70 (2.04)	-0.19 (-0.33, -0.05)	7.53 (2.91)	7.00 (2.51)	0.53 (0.6)
...median [IQR]	6.00 [5.00, 8.00]	6.00 [5.00, 8.00]	-	5.00 [4.00, 7.00]	5.00 [4.00, 7.00]	-	7.00 [5.00, 9.00]	7.00 [5.00, 9.00]	-

- Report summary parameters of study population

	Optum	MarketScan	Medicare
Variable	Value	Value	Value
Number of patients in full cohort	6,946	3,694	8,031
Number of patients dropped as incomplete cases	0	0	2
Number of patients that did not begin follow-up	16	5	7
Number of patients in analytic cohort	6,930	3,689	8,022

Number of events	1435	592	1992
Number of person-years	3,277.04	1,877.04	3,093.20
Number of patients in group: ACE Inhibitors - Reference	4,208	2,216	6,286
Number of patients in group: Sacubitril/Valsartan - Exposure	2,722	1,473	1,736
Risk per 1,000 patients	207.07	160.48	248.32
Rate per 1,000 person-years	437.9	315.39	643.99

- Report median follow-up time by treatment group

Patient Group	Optum Median Follow-Up Time (Days) [IQR]	Marketscan Median Follow-Up Time (Days) [IQR]	Medicare Median Follow-Up Time (Days) [IQR]
Overall Patient Population	95 [43, 213]	117 [58, 242]	82 [39, 173]
Referent - ACE Inhibitors	99 [42, 209]	118 [58, 240]	81 [38, 170]
Exposure - Sacubitril/Valsartan	92 [44, 217]	111 [57, 246]	86 [45, 183]

- Report reasons for censoring in the overall study population

	Optum	Marketscan	Medicare
Overall	6930	3689	8022
Outcome	1,361 (19.6%)	558 (15.1%)	1,933 (24.1%)
Start of an additional exposure	252 (3.6%)	155 (4.2%)	156 (1.9%)
End of Index Exposure	2,445 (35.3%)	1,264 (34.3%)	2,078 (25.9%)
Specified date reached	1,101 (15.9%)	721 (19.5%)	1,964 (24.5%)
End of patient data	0 (0.0%)	0 (0.0%)	0 (0.0%)
End of patient enrollment	645 (9.3%)	713 (19.3%)	691 (8.6%)
Switch to ARBs or Aliskiren + Nursing Home admission Occurred	1,126 (16.2%)	278 (7.5%)	1,200 (15.0%)

## 8 Initial Power Assessment

### Action report name:

Optum- <https://bwh-dope.aetion.com/projects/details/1069/results/61862/result/0>

Marketscan- <https://bwh-dope.aetion.com/projects/details/1072/results/61853/result/0>

Medicare- <https://bwh-dope.aetion.com/projects/details/1073/results/61855/result/0>

### Date conducted: 11/24/2020

In order to complete the initial power analysis, the dummy outcome of a 90-day gap in database enrollment will be used. Complete a 1:1 PS-matched comparative analysis using this outcome. PS should include only 3 covariates: age, sex, and combined comorbidity index.

- In the appropriate excel sheet below, report number of patients matched in each treatment group. Input the overall risk of outcome from Section 7. Input the desired or assumed HR, alpha level, and non-inferiority margin (if applicable) from the RCT (Section 1.3.1). The number of expected events and corresponding power are then calculated automatically. If the study is to be implemented in more than one database, copy and paste excel sheet to report power for each database separately and for the pooled analysis that uses data from all databases together.

	Optum	Marketscan	Medicare	Pooled
Number of people matched				
Reference	2722.0	1468.0	1736.0	5926.0
Exposure	2722.0	1468.0	1736.0	5926.0
Risk per 1,000 patients	207.1	160.5	248.3	--
Rate per 1,000 person-years	437.9	315.4	644.0	
N of events	1,435	592	1,992	4,019
N of patients (both groups) at Step 1	6,946	3,694	8,031	18,671
Risk per 1,000 patients	206.6	160.3	248.0	215.3

Superiority Analysis (Pooled)	
Number of patients matched	
Reference	5,926
Exposed	5,926
Risk per 1,000 patients	215.25
Desired HR from RCT	0.8
Alpha (2-sided)	0.05
Number of events expected	2551.143
Power	0.99988126

Superiority Analysis (Optum)	
Number of patients matched	
Reference	2,722
Exposed	2,722
Risk per 1,000 patients	207.10
Desired HR from RCT	0.8
Alpha (2-sided)	0.05
Number of events expected	1127.4524
Power	0.9629782

Superiority Analysis (MarketScan)	
Number of patients matched	
Reference	1,468
Exposed	1,468
Risk per 1,000 patients	160.50
Desired HR from RCT	0.8
Alpha (2-sided)	0.05
Number of events expected	471.228
Power	0.677969637

Superiority Analysis (Medicare)	
Number of patients matched	
Reference	1,736
Exposed	1,736
Risk per 1,000 patients	248.30
Desired HR from RCT	0.8
Alpha (2-sided)	0.05
Number of events expected	862.0976
Power	0.905904762

- Stop analyses until feasibility and power are reviewed by primary investigators, FDA, and assigned members of advisory board.

Reviewed by PI:	[name]	Date reviewed:	12/2/20
Reviewed by FDA:	[name]	Date reviewed:	12/8/20
Reasons for stopping analysis (if required):			

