### 1.4 Required power for primary endpoint and noninferiority margin (if applicable)

After following 8000 patients for 34 months, at an overall two-sided alpha level of 0.05, the primary end point would occur in 2410 patients, which would provide a power of 97% to detect a 15% reduction in the risk of this outcome.

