## 6. Final Power Assessment

Date conducted: 12/22/2020

- Re-calculate power in the appropriate excel table, using the revised number of matched patients from the PS-match in Section 9. All other parameters in the table should be the same as in Section 8.

Superiority Analysis (Pooled)	
Number of patients matched	
Reference	3,033
Exposed	3,033
Risk per 1,000 patients	215.25
Desired HR from RCT	0.8
Alpha (2-sided)	0.05
Number of events expected	1305.7065
Power	0.980850168

Superiority Analysis (Optum)	
Number of patients matched	
Reference	1,279
Exposed	1,279
Risk per 1,000 patients	206.60
Desired HR from RCT	0.8
Alpha (2-sided)	0.05
Number of events expected	528.4828
Power	0.727390963

Superiority Analysis ( Marketscan )	
Number of patients matched	
Reference	748
Exposed	748
Risk per 1,000 patients	160.30
Desired HR from RCT	0.8
Alpha (2-sided)	0.05
Number of events expected	239.8088
Power	0.408308308

Superiority Analysis (Medicare)	
Number of patients matched	
Reference	1,006
Exposed	1,006
Risk per 1,000 patients	248.30
Desired HR from RCT	0.8
Alpha (2-sided)	0.05
Number of events expected	499.5796
Power	0.703266933

- Stop analyses until balance and final power assessment are reviewed by primary investigators, FDA, and assigned members of advisory board.

Reviewed by PI:	[name]	Date reviewed:	12/26/20
Reviewed by FDA:		Date reviewed:	
Reasons for stopping analysis (if required):			

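### Pooled expected events in both power tables exceed the sum of their own database rows, because the pooled risk carries unmatched weights; the effect on power is small

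*Protocol*

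**What the plan says.** Section 8 (Initial Power Assessment) tells the analyst, where more than one database is used, to "copy and paste excel sheet to report power for each database separately and for the pooled analysis that uses data from all databases together", and gives the risk input as "Input the overall risk of outcome from Section 7". Section 7 reports a risk for each database and no pooled risk.

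The Section 8 table lists matched patients per arm as "Reference 2722.0 1468.0 1736.0 5926.0" (Optum, MarketScan, Medicare, pooled). Its first risk row reads "Risk per 1,000 patients 207.1 160.5 248.3", with the pooled cell left empty. Lower rows give 4,019 events among 18,671 patients before matching, and a second set of risks: 206.6, 160.3 and 248.0, with 215.3 pooled. Every power table uses "Desired HR from RCT 0.8" and "Alpha (2-sided) 0.05".

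The Final Power Assessment (printed as section 6, after Section 9) replaces the matched counts with 1,279, 748 and 1,006 per arm, 3,033 pooled. It adds: "All other parameters in the table should be the same as in Section 8".

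**The concern.** The pooled analysis contains the same matched patients as the three database analyses and no others. With one outcome and one set of risks, its expected events must be the sum of the three database figures. In both tables it is larger, so the tables contradict themselves.

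The final table also departs from its own rule. Compared with the Section 8 power tables, Optum's risk moves from 207.10 to 206.60 and MarketScan's from 160.50 to 160.30, while Medicare's stays at 248.30.

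These figures go to the investigators, the FDA and the advisory board members at two points where analysis stops for review. An event count that cannot be rebuilt from the rows beneath it should be corrected there, even if the effect on power is slight.

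**Working it through.** **Inputs.** Matched patients per arm, risks, hazard ratio 0.80 and two-sided alpha 0.05 are from the Section 8 and Final Power Assessment tables. Cohort sizes and event counts are from Sections 7 and 8.

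**Formulas.** Expected events D = 2 × matched patients per arm × risk / 1,000. Power = Φ(√(D/4) × |ln 0.80| − 1.96), with |ln 0.80| = 0.2231.

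**Reproducing the printed figures.** All eight rows are recovered, events exactly and power to about 0.0001. For the pooled rows:
- Section 8: 2 × 5,926 × 0.21525 = 2,551.143 events; power 0.99988.
- Final: 2 × 3,033 × 0.21525 = 1,305.7065 events; power 0.98085.

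The method is therefore known, and only the pooled risk is in question.

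**Summing the database rows as printed.**

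| | Optum | MarketScan | Medicare | Sum | Pooled row | Excess |
|---|---|---|---|---|---|---|
| Section 8 | 1,127.45 | 471.23 | 862.10 | 2,460.78 | 2,551.14 | 90.4 (3.7% of the sum) |
| Final | 528.48 | 239.81 | 499.58 | 1,267.87 | 1,305.71 | 37.8 (3.0% of the sum) |

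**Cause.** 4,019 / 18,671 = 215.25 per 1,000. This average weights each database by its share of the cohort before matching:

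| Share of patients | Optum | MarketScan | Medicare |
|---|---|---|---|
| Before matching (6,946 / 3,694 / 8,031) | 37.2% | 19.8% | 43.0% |
| Section 8 match (2,722 / 1,468 / 1,736) | 45.9% | 24.8% | 29.3% |
| Final match (1,279 / 748 / 1,006) | 42.2% | 24.7% | 33.2% |

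Medicare has the highest risk and loses most share in matching. The pooled risks implied by the database rows are 2,460.78 / 11,852 = 207.6 and 1,267.87 / 6,066 = 209.0 per 1,000.

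**Effect on power at hazard ratio 0.80.**
- Section 8: 2,460.78 events give 0.99982 against the printed 0.99988, a difference of 0.006 percentage points.
- Final: 1,267.87 events give √(1,267.87/4) × 0.2231 − 1.96 = 2.013, so power is 0.9779 against 0.9809, a difference of 0.29 points.

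**Risk basis.** The Section 8 power tables by database use the analytic cohort; for Optum, 1,435 / 6,930 = 207.07. The second risk row in Section 8 uses the full cohort; for Optum, 1,435 / 6,946 = 206.6. The final table takes full-cohort values for Optum and MarketScan and the analytic-cohort 248.3 for Medicare, whose full-cohort value is 248.0. That one cell is worth 2 × 1,006 × 0.0003 = 0.6 events. On a single basis:

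| | Section 8 events | Power | Final events | Power |
|---|---|---|---|---|
| Full cohort (206.6 / 160.3 / 248.0) | 2,456.4 | 99.98% | 1,267.3 | 97.8% |
| Analytic cohort (207.1 / 160.5 / 248.3) | 2,460.8 | 99.98% | 1,269.4 | 97.8% |

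The choice of basis makes no practical difference, but the tables should use only one.

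**The case against.** The strongest reply is that the pooled row follows the instruction to use the overall risk, shows openly how 215.3 was derived, and serves only as a feasibility screen; a crude average is then a choice and not a formula error. It is true that the formula is sound. But Section 7 prints no pooled risk, so the instruction does not call for unmatched weights, and the result still disagrees with the rows beside it.

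A second reply is that 206.6 and 160.3 already stand in the lower part of the Section 8 table, so using them later arguably respects the rule on unchanged parameters. On that reading Medicare's 248.3 is the odd cell. One table is inconsistent either way, by a trivial amount.

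The reply on consequence stands in full: the shift in power is negligible, and the documents set no numerical cut-off that it could cross.

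Two stronger readings are tempting and are not supported:
- A reader might set the final pooled power against the trial design in Section 1.4, "which would provide a power of 97% to detect a 15% reduction in the risk of this outcome", and infer that a required power is missed at that smaller effect. Section 1.4 belongs to the summary of the RCT and describes that trial's own design. Nothing makes 97% a threshold for this study, and Section 8 allows the desired or assumed hazard ratio from the RCT; 0.80 matches the trial estimate in Section 1.5.
- A reader might also adjust the risks for the larger ACE inhibitor share before matching. That needs outcome risks by arm, which the documents do not give.

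**Conclusion.** The point holds as a minor arithmetic inconsistency. Pooled expected events are overstated by 90.4 (3.7%) in Section 8 and by 37.8 (3.0%) in the Final Power Assessment, because unmatched weights are applied to matched patients. The final table also mixes two risk bases. Pooled power is overstated by 0.006 and 0.29 percentage points. Neither shift would alter a feasibility decision.

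The corrected 97.8% should not be read as the study's true power. It keeps the printed formula, a hazard ratio of 0.80 and the Section 7 risks. Those risks come from the cohort before matching, whose median follow-up (95, 117 and 82 days) is shorter than that of the final matched sets in Section 9 (118, 139 and 102 days). Section 7 also lists 4,019 events in one table and 1,361 + 558 + 1,933 = 3,852 patients whose follow-up ended with the outcome in another. The correction makes the tables agree with themselves and does no more than that.

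**What to change.** Choose one risk basis, full or analytic cohort, and use it in every row of both power tables. Set pooled expected events to the sum over databases of matched patients times that database's risk, and show the resulting matched-weighted risk in place of 215.25. The restated pooled rows are:
- Section 8: about 2,456 to 2,461 events, power 99.98%.
- Final Power Assessment: about 1,267 to 1,269 events, power 97.8% at hazard ratio 0.80.

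If the final table keeps a basis different from the Section 8 power tables, amend the sentence saying that the other parameters are unchanged. The cost is a spreadsheet edit with no new data or analysis, and one printed power becomes slightly less favourable.

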## 9. Balance Assessment

Optum- <https://bwh-dope.aetion.com/projects/details/1069/results/63131/result/0>

MarketScan- <https://bwh-dope.aetion.com/projects/details/1072/results/63129/result/0>

Medicare- <https://bwh-dope.aetion.com/projects/details/1073/results/63128/result/0>

Date conducted: 12/22/2020

After review of initial feasibility and power analyses, complete creation of the remaining covariates from Section 6.2. Again, using the

dummy outcome of a 90-day gap in database enrollment, complete a 1:1 PS-matched analysis. The PS should include the complete list of covariates.

- Provide plot of PS distributions stratified by treatment group.

Note- Please refer to **Appendix B**.

- Report covariate balance after matching.

Note- For Table 1, please refer to **Appendix B**.

- Report reasons for censoring by treatment group.

	Overall	Referent	Exposure
Dummy outcome	0 (0%)	0 (0%)	0 (0%)
Death	150 (2.47%)	64 (2.11%)	86 (2.84%)
Start of an additional exposure	309 (5.09%)	106 (3.49%)	203 (6.69%)
End of Index Exposure	2285 (37.67%)	1206 (39.76%)	1079 (35.58%)
Specified date reached	1868 (30.79)	879 (28.98%)	989 (32.61%)
End of patient enrollment	696 (11.47%)	366 (12.07%)	330 (10.88%)
Switch to ARBs or Aliskiren + Nursing Home admission Occurred	758 (12.50%)	412 (13.58%)	346 (11.41%)

- Report follow-up time by treatment group.

Patient Group	Optum Median Follow-Up Time (Days) [IQR]	MarketScan Median Follow-Up Time (Days) [IQR]	Medicare Median Follow-Up Time (Days) [IQR]
Overall Patient Population	118 [58, 286]	139 [59, 296]	102 [46, 189]
Referent - ACE Inhibitors	126 [60, 309]	142 [77, 295]	102 [42, 170]
Exposure - Sacubitril/Valsartan	108 [56, 266]	136 [58, 300]	106 [58, 218]

- Report overall risk of the primary outcome.

	Optum	MarketScan	Medicare	Pooled
Risk per 1,000 patients	206.6	160.3	248.0	215.3

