### 5.2 Important steps for cohort formation

New users (defined as no use of sacubitril/valsartan in 180 days prior to index date) of the exposure will be identified. New users of a comparator drug were identified as patients with no ACEi fills during the 60 days prior to the index date to allow for patients who are switching among ACEi drugs or restarting ACEi after a brief lapse.

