## 6 Variables

### 6.1 Exposure-related variables:

#### Study drug:

The study exposure of interest is initiation of sacubitril/valsartan (ARNI) at any dose and frequency. Initiation will be defined by no use of sacubitril/valsartan during the prior 180 days before treatment initiation (washout period). Patients are required to be incident users with respect to their exposure group only, since one of the RCT inclusion criteria was prior treatment with ACEi or ARB.

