# Appendix A

		Measured 365 days prior to drug initiation in any diagnosis position and inpatient care setting	
4b	Hospitalization for heart failure within the last 12 months	
Hospital Admission for CHF
 
ICD-9 diagnosis: 428.x, 398.91, 402.01, 402.11, 402.91, 404.01, 404.11, 404.91, 404.03, 404.13, 404.93
 
ICD-10 diagnosis: I50.1, I50.2x, I50.4, I50.814, I09.81, I11.0, I13.0, I13.2
	
5	Treatment with a stable dose of an ACE inhibitor or an ARB equivalent to enalapril 10 mg/day for at least 4 weeks before the screening visit; and treatment with a stable dose of a beta-blocker for at least 4 weeks prior to the screening visit, unless contraindicated or not tolerated	
Measured 47 days to 2 days prior to drug initiation in prescription claims requiring 28 days supply of oral ACEi or ARB -
 
ACE inhibitors' generic names for prescription claims: Enalapril, Captopril, Clazapril, Fosinopril, Lisinopril, Moexipril, Perindopril, Quinapril, Trandolapril, Zofenopril, Benazepril
 
-OR-
 
ARBs generic names for prescription claims: Candesartan, Eprosartan, Irbesartan, Losartan, Olmesartan, Telmisartan, Valsartan, Azilsartan
	
5a	Treatment with a stable dose of an ACE inhibitor or an ARB equivalent to enalapril 10 mg/day for at least 4 weeks before the screening visit	AND the following:	
5b	Treatment with a stable dose of a beta-blocker for at least 4 weeks prior to the screening visit, unless contraindicated or not tolerated	
Measured 45 days prior to index drug initiation in prescription claims (generic names) of an oral beta-blocker for at least 4 weeks (28 days)
 
Beta-blocker generic names for prescription claims: Acebutolol, Atenolol, Betaxolol, Bisoprolol, Carvedilol, Esmolol, Labetalol, Metoprolol, Metiranolol, Nebivolol, Nadolol, Propranolol, Pindolol, Sotalol, Penbutolol, Oxprenolol
	
6	Although not required, the protocol specified that an aldosterone antagonist should also be considered in all patients, taking account of renal function, serum potassium, and tolerability. If given, the dose of aldosterone antagonist should be stable for at least 4 weeks prior to the screening visit		
EXCLUSION CRITERIA			

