# Appendix A

11	ACE inhibitor	Prescription claims for: Benazepril, captopril, enalapril, fosinopril, lisinopril, moexipril, perindopril, quinapril, ramipril, trandolapril	0.221748	Measured 180 days prior to and including the date of index drug initiation	6 months prior to index date + index date + 30days post-index
12	Index diagnosis recorded during an outpatient visit	Any diagnosis position in an outpatient care setting ICD-9 diagnosis: 428.x, 398.91, 402.01, 402.11, 402.91, 404.01, 404.11, 404.91, 404.03, 404.13, 404.93 ICD-10 diagnosis: I50.1, I50.2x, I50.4x, I50.814, I09.81, I11.0, I13.0, I13.2	-0.187191	Measured between 180 days prior to and including the date of drug initiation and pick claim closest to the index initiation	on index date
13	Mineralocorticoid receptor antagonist	Prescription claims for: Eplerenone, spironolactone	0.166008	Measured 180 days prior to and including the date of index drug initiation	6 months prior to index date + index date + 30days post-index
14	Anemia	ICD-9 diagnosis: 280.xx - 285.xx ICD-10 diagnosis: Please copy from ICD-10 codes tabs for anemia	-0.165353	Measured 180 days prior to and including the date of index drug initiation	6 months prior to index date + index date + 30days post-index
15	Valve disorder	ICD-9 diagnosis: 394.x - 397.x, 398.9x, V42.2, V43.3 ICD-10 diagnosis: Please copy from ICD-10 codes tabs for valve disorder ICD-9 procedure: 35.1x, 35.2x ICD-10 procedure: Please copy from ICD-10 codes tabs for valve disorder CPT code: 33660-33665, 33400-33403, 33420-33430, 33460, 33463-33468, 33475, 33496, 0257T, 0258T, 0259T, 0262T	-0.163684	Measured 180 days prior to and including the date of index drug initiation	6 months prior to index date + index date + 30days post-index
16	Digoxin	Prescription claims for: Digoxin	0.163224	Measured 180 days prior to and including the date of index drug initiation	6 months prior to index date + index date + 30days post-index
17	Thiazide diuretic	Prescription claims for: Bendroflumethiazide, Benztiazide, Chlorothiazide, Chlorthalidone, Hydrochlorothiazide, Indapamide, Methyclothiazide, Metolazone, Polythiazide, Quinethazone, Trichlormethiazide	-0.160819	Measured 180 days prior to and including the date of index drug initiation	6 months prior to index date + index date + 30days post-index

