...median (IQR)	15.93 [5.74, 32.88]	18.14 [6.52, 33.73]	-0.0600	10.53 [3.58, 20.38]	12.40 [5.11, 19.94]	-0.1150	16.10 [5.26, 32.03]	18.78 [5.57, 34.95]	-0.0796	14.65 (36.11)	16.94 (26.88)	-0.0719
SES Proxy - Low income indicator; n (%)	275 (21.5%)	299 (23.4%)	-0.0455	0 (0.0%)	0 (0.0%)	#DIV/0!	0 (0.0%)	0 (0.0%)	#DIV/0!	275 (9.1%)	299 (9.9%)	-0.0273
SES Proxy - Business type												
...Commercial; n (%)	325 (25.4%)	340 (26.6%)	-0.0274	0 (0.0%)	0 (0.0%)	#DIV/0!	0 (0.0%)	0 (0.0%)	#DIV/0!	325 (10.7%)	340 (11.2%)	-0.0160
...Medicare; n (%)	954 (74.6%)	939 (73.4%)	0.0274	0 (0.0%)	0 (0.0%)	#DIV/0!	0 (0.0%)	0 (0.0%)	#DIV/0!	954 (31.5%)	939 (31.0%)	0.0108
SES Proxy - Insurance Plan type												
...Comprehensive; n (%)	0 (0.0%)	0 (0.0%)	#DIV/0!	105 (14.0%)	94 (12.6%)	0.0412	0 (0.0%)	0 (0.0%)	#DIV/0!	105 (3.5%)	094 (3.1%)	0.0224
...HMO; n (%)	0 (0.0%)	0 (0.0%)	#DIV/0!	62 (8.3%)	71 (9.5%)	-0.0422	0 (0.0%)	0 (0.0%)	#DIV/0!	062 (2.0%)	071 (2.3%)	-0.0207
...PPD; n (%)	0 (0.0%)	0 (0.0%)	#DIV/0!	403 (53.9%)	400 (53.5%)	0.0080	0 (0.0%)	0 (0.0%)	#DIV/0!	403 (13.3%)	400 (13.2%)	0.0029
...Others; n (%)	0 (0.0%)	0 (0.0%)	#DIV/0!	178 (23.8%)	183 (24.5%)	-0.0164	0 (0.0%)	0 (0.0%)	#DIV/0!	178 (5.9%)	183 (6.0%)	-0.0042
SES Proxy - Dual status code (with Medicaid); n (%)	0 (0.0%)	0 (0.0%)	#DIV/0!	0 (0.0%)	0 (0.0%)	#DIV/0!	202 (20.1%)	203 (20.2%)	-0.0025	202 (6.7%)	203 (6.7%)	0.0000

\*Excluded from P5 model: Age Categories, Use of Lithium, Use of AGI & Meglitinides, PCSK9 Inhibitors, Use of heparin or LMWH, Hemodialysis/Peritoneal dialysis

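### The propensity-score match drops every sacubitril/valsartan initiator without an ACE-inhibitor record (2,301 of 5,371); the protocol does not state this narrower population, and the pooled balance column misreports it

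*Protocol*

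**What the plan says.** Section 9 (Balance Assessment) asks for a 1:1 PS match and says: "The PS should include the complete list of covariates". The footnote to the Appendix B table lists what was left out: "Age Categories, Use of Lithium, Use of AGI & Meglitinides, PCSK9 Inhibitors, Use of heparin or LMWH, Hemodialysis/Peritoneal dialysis". The row for ACE inhibitors among the cardiovascular medications is not on that list and carries no asterisk.

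The population is described more broadly. Section 6.1 requires new use of the patient's own exposure group only, "since one of the RCT inclusion criteria was prior treatment with ACEi or ARB". Inclusion #5/5a in Appendix A likewise accepts an ACEi or an ARB: "Measured 47 days to 2 days prior to drug initiation in prescription claims requiring 28 days supply of" either class.

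Appendix B prints no window for the ACEi row. Two other windows in the protocol include the index date. In Section 6.2 the comorbidity index is "measured over the default baseline covariate assessment period of 180 days prior to and including the index prescription date". In the ejection-fraction algorithm of Appendix A the ACEi predictor is "Measured 180 days prior to and including the date of index drug initiation".

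Section 5.2 defines reference new users by "no ACEi fills during the 60 days prior to the index date".

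**The concern.** A covariate that takes one value throughout an arm cannot be balanced by matching. It can only remove the patients in the other arm who have the other value. Here every reference patient has ACEi = 1, so a patient with ACEi = 0 is an initiator with certainty. The fitted PS for such patients tends to 1, and no reference patient shares it.

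Two things are at stake. First, the matched estimate answers a question about initiators with an ACEi record, while the text describes prior ACEi-or-ARB users. Second, the protocol stops analyses until balance and final power have been reviewed, and the pooled balance column put to that review gives wrong figures for this covariate.

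**Working it through.** **Inputs.** Appendix B, before and after matching: numbers of patients and the rows for ACE inhibitors and ARBs. Final Power Assessment: pairs, risk, HR and alpha.

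**The plan's own power figure.** Events = 2 × 3,033 × 0.21525 = 1,305.7. By Schoenfeld's formula with HR 0.8, equal allocation and two-sided alpha 0.05, power = Φ(√(1,305.7 × 0.25) × |ln 0.8| − 1.96) = Φ(2.07) = 0.981, which agrees with the printed 0.980850168.

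**Initiators with and without an ACEi record.**

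| | Optum | MarketScan | Medicare | Sum |
|---|---|---|---|---|
| Reference with record, before matching | 17,244 of 17,244 | 10,721 of 10,721 | 18,303 of 18,303 | 46,268 of 46,268 |
| Initiators before matching | 2,424 | 1,289 | 1,658 | 5,371 |
| With ACEi record | 1,288 (53.1%) | 764 (59.3%) | 1,018 (61.4%) | 3,070 (57.2%) |
| Without (difference) | 1,136 | 525 | 640 | 2,301 (42.8%) |
| Matched initiators | 1,279 | 748 | 1,006 | 3,033 |
| Matched with ACEi record | 1,279 (100.0%) | 748 (100.0%) | 1,006 (100.0%) | 3,033 (100%) |

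All matched initiators have a record, so all 2,301 without one are among the 5,371 − 3,033 = 2,338 unmatched. The printed standardised differences show the same pattern: 1.3291, 1.1716 and 1.1213 before matching, and a division by zero afterwards.

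**ARB use among initiators.** The Medicare count before matching prints as 172. It is read as 727, from its 43.8% of 1,658 and from the pooled 1,998 − 1,271.

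- Before: 1,271 + 629 + 727 = 2,627 of 5,371 (48.9%).
- After: 127 + 92 + 81 = 300 of 3,033 (9.9%).

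**Pooled ACEi row.** The numerators are Optum plus Medicare; the denominators include MarketScan.

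| | Printed | With MarketScan |
|---|---|---|
| Reference, before | 17,244 + 18,303 = 35,547 (76.8%) | 46,268 (100%) |
| Initiators, before | 1,288 + 1,018 = 2,306 (42.9%) | 3,070 (57.2%) |
| Each arm, after | 1,279 + 1,006 = 2,285 (75.3%) | 3,033 (100%) |

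The pooled standardised difference before matching prints as 0.7370. With the corrected proportions it is (1 − 0.5716) / √(0.5716 × 0.4284 / 2) = 1.22. The pooled ARB row has the same omission: it prints 37.2% and 6.9% for initiators, where the sums give 48.9% and 9.9%.

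**The case against.** Losing patients outside the area of overlap is an ordinary result of matching, and the database columns of Appendix B do print 100.0% in both matched arms. Exclusion #7 mentions an enalapril run-in in the trial, so an ACEi-experienced group may be close to the patients randomised. Pooled power remains high. All of this stands. It makes the restriction defensible, but it neither states it nor corrects the pooled figures.

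Four stronger readings are tempting, and the document does not support them.

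- *The ACEi term alone explains the loss.* Of the 3,070 initiators with a record only 37 are unmatched, so a reader might infer that all other covariates cost at most 37 pairs. That count is conditional on the ACEi term being in the model. ARB use is also strongly separating: 52.4%, 48.8% and 43.8% of initiators against 3.3%, 3.2% and 4.4% of the reference arm. By subtraction, 2,627 − 300 = 2,327 of the 2,338 unmatched initiators have an ARB record, so many might stay unmatched without the ACEi term. The 5,926 pairs in Section 8 do not settle it: that match used only age, sex and the comorbidity index, in a different cohort.
- *The reference patient's own index fill produced the 100%.* This is possible, since windows elsewhere include the index date. Appendix B prints none for this row, and true earlier use may account for much of it.
- *The 100%/100% row conceals a real difference in prior treatment.* That depends on rules that are hard to fit together. Suppose Inclusion #5a governed this cohort and the ARB covariate covers days −47 to −2. Then at least 3,033 − (118 + 89 + 75) = 2,751 matched reference patients (90.7%) had real ACEi supply, and the row is roughly right. If the 60-day rule in Section 5.2 shaped the reference arm instead, it may not be.
- *A corrected window would recover a calculable number of pairs.* Any such bound assumes exact matching on ACEi status, whereas Section 9 specifies matching on the score.

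**Conclusion.** The point holds for the unstated population and for the pooled figures. All 2,301 of 5,371 initiators without an ACEi record (42.8%) are unmatched, and the matched exposed arm consists only of initiators with a record. Its ARB use is 9.9%, against 48.9% before matching. The text describes prior ACEi-or-ARB users and nowhere states the restriction. The pooled ACEi row is wrong both before and after matching.

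The ACEi counts rest only on printed cells. The ARB percentage before matching also rests on reading the Medicare count as 727. That the ACEi covariate was in the PS follows from the instruction in Section 9 and its absence from the list of exclusions. Having a record does not exclude ARB use: 300 matched initiators have both. The role of the index fill is a possibility only. Pooled power of 0.981 for 3,033 pairs is correctly calculated and is not affected by this point as it stands.

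**What to change.** 1. Correct the pooled columns of Appendix B so that MarketScan is in the numerators, before the balance review. For the ACEi row this gives 46,268 (100%) and 3,070 (57.2%) before matching, and 3,033 (100%) in each arm after.
2. State in Section 9, and wherever the estimate is described, that the matched comparison applies to initiators with an ACEi record and not to all prior ACEi-or-ARB users.
3. State the window of the ACEi and ARB covariates. If it includes the index date, end it at day −1, so that a reference patient's own index fill cannot set the covariate. Then re-match and re-issue the Appendix B table and the power table.
4. Reconcile the 60-day rule in Section 5.2 with the day −47 to −2 window of Inclusion #5a, since together they decide how much true prior ACEi use the reference arm has.

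Items 1 and 2 cost a table correction and a sentence. Item 3, if needed, costs one re-run. The number of pairs may then rise, stay the same or fall; the protocol gives nothing to bound the change. If initiators without prior ACEi use still have no match, the statement in item 2 remains.
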